## 9.2 Operational definitions for (S)AEs

(S)AEs will be defined according to standard definitions, section 9.1.

## 9.3 Recording and reporting of SAEs AND SUSARs

The period of time over which AEs, ARs, SAEs, SARs and SUSARs are to be monitored start at and finish at:

- For AEs / SAEs – 1st MP dose to day 30 post operation
- For ARs / SARs and SUSARs – 1st MP dose to day 30 post operation

SAEs occurring in a research participant should be reported to the main REC/Sponsor where in the opinion of the Chief Investigator (CI) the event was:

- Related – that is, it resulted from administration of any of the research procedures, and
- Unexpected – that is, the type of event is not listed in the protocol as an expected occurrence.

Adverse events which are expected occurrences and relevant to the study population includes but is not limited to (multiple post-operative complications occur routinely in this cohort undergoing extensive colorectal surgery):

- Those listed in the Summary of Product Characteristics
- Surgical site infections
- All other infections including respiratory, urinary and skin infections (including fungal infections).
- Vascular events e.g. emboli, thrombosis, haemorrhage
- Failure of the surgical procedure e.g. anastomotic breakdown, fistulation
- Procedures i.e. urinary catheterisation, venous access device.

**SUSARs** occurring from the time of **randomisation** until 30 days post cessation of trial treatment must be recorded on the AE form and faxed to the Sponsor within one working day of the research staff becoming aware of the event. Once all resulting queries have been resolved, the Sponsor will request the original form should also be posted to the Sponsor and a copy to be retained on site.

For each **SUSARs** the following information will be collected:

- full details in medical terms and case description
- event duration (start and end dates, if applicable)
- action taken
- outcome

- seriousness criteria
- causality (i.e. relatedness to trial drug / investigation), in the opinion of the investigator
- whether the event would be considered expected or unexpected.

Any change of condition or other follow-up information should be faxed to the Sponsor as soon as it is available or at least within one working day of the information becoming available.

SUSARs will be reported to the REC using the online reporting form within 15 days. Events will be followed up until the event has resolved or a final outcome has been reached, or 30 days have passed. The data monitoring committee will also be given a combined report of all the AEs, SAEs, ARs, SARs and SUSARs at the meeting. Any AEs with rates higher than expected will reported to the REC and sponsor.

All SUSARs and will be subject to expedited reporting to the Medicines and Healthcare Products Regulatory Agency (MHRA). The PI or delegate will inform the MHRA, the REC and the Sponsor of SUSARs within the required expedited reporting timescales.

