## 9 PHARMACOVIGILANCE

### 9.1 Definitions

Term	Definition
Adverse Event (AE)	Any untoward medical occurrence in a participant to whom a medicinal product has been administered, including occurrences which are not necessarily caused by or related to that product.
Adverse Reaction (AR)	
An untoward and unintended response in a participant to an medicinal product which is related to any dose administered to that participant.
 
The phrase "response to an medicinal product" means that a causal relationship between a trial medication and an AE is at least a reasonable possibility, i.e. the relationship cannot be ruled out.
 
All cases judged by either the reporting medically qualified professional or the Sponsor as having a reasonable suspected causal relationship to the trial medication qualify as adverse reactions.

Serious Adverse Event (SAE)	
A serious adverse event is any untoward medical occurrence that:
 
 
• results in death
 
• is life-threatening
 
• requires inpatient hospitalisation or prolongation of existing hospitalisation
 
• results in persistent or significant disability/incapacity
 
• consists of a congenital anomaly or birth defect
 
 
Other 'important medical events' may also be considered serious if they jeopardise the participant or require an intervention to prevent one of the above consequences.
 
NOTE: The term "life-threatening" in the definition of "serious" refers to an event in which the participant was at risk of death at the time of the event; it does not refer to an event which hypothetically might have caused death if it were more severe.

Serious Adverse Reaction (SAR)	An adverse event that is both serious and, in the opinion of the reporting Investigator, believed with reasonable probability to be due to one of the trial treatments, based on the information provided.
Suspected Unexpected Serious Adverse Reaction (SUSAR)	
A serious adverse reaction, the nature and severity of which is not consistent with the information about the medicinal product in question set out:
 
 
• in the case of a product with a marketing authorisation, in the summary of product characteristics (SmPC) for that product
 
• in the case of any other medicinal product, in the investigator's brochure (IB) relating to the trial in question
 

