## 9.4 Responsibilities

### Principal Investigator (PI):

Checking for AEs and ARs when participants attend for treatment / follow-up.

1. Using medical judgement in assigning seriousness, causality and expectedness using the Reference Safety Information approved for the trial.
2. Ensuring that all planned recording and reporting procedures for SAEs AND SUSARs as detailed in section 9.3 are adhered to. Ensuring that SUSARs are chased with Sponsor if a record of receipt is not received within 2 working days of initial reporting.

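### Sections 9.1 and 9.3 test expectedness differently, so the same related serious event can be a SUSAR under one and expected under the other

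*Combined protocol and SAP*

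**What the plan says.** Three places in section 9 bear on whether a serious event counts as expected.

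- **Section 9.3, rule for serious adverse events.** An event "should be reported to the main REC/Sponsor where in the opinion of the Chief Investigator (CI) the event was" both related and unexpected. Related means that "it resulted from administration of any of the research procedures". Unexpected means that "the type of event is not listed in the protocol as an expected occurrence". The list that follows is introduced by "Adverse events which are expected occurrences and relevant to the study population includes but is not limited to". Its entries are "Those listed in the Summary of Product Characteristics", surgical site infections, all other infections, vascular events (emboli, thrombosis, haemorrhage), failure of the surgical procedure, and procedures such as catheterisation and venous access. No entry carries a limit on severity or outcome.
- **Section 9.1, SUSAR definition.** A serious reaction to the product counts as a SUSAR if it is one "the nature and severity of which is not consistent with the information about the medicinal product in question set out". For a product with a marketing authorisation, the reference is the SmPC.
- **Section 9.4, Principal Investigator's duties.** The Principal Investigator assigns "expectedness using the Reference Safety Information approved for the trial". Section 9 does not say what document that is. The same list of duties requires the reporting procedures of 9.3 to be followed. The Chief Investigator's duties in 9.4 include assigning expectedness by medical judgement, with no reference named.

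Section 9.3 also has a separate SUSAR route: to the sponsor within one working day, to the REC within 15 days, and to the MHRA on an expedited basis. It gives the data monitoring committee a combined report of all events and reactions, and sends to the REC and sponsor any adverse events whose rates are higher than expected.

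**The concern.** Expectedness decides whether a related serious event is reported individually and quickly. Here two rules decide it on different criteria (type, against nature with severity) and from different references (a protocol list, against the SmPC). The protocol list is also left open, so its limits are unclear.

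The gap falls where this trial would want a clear signal. Section 2.1 names the higher cefuroxime dose as the risk above standard treatment. Section 2, under the minimum clinically important difference, names thrombophlebitis, vascular access complications, *C. difficile* and antibiotic resistance as possible, though not expected, harms. Apart from resistance, these plausibly fall within the vascular, procedure and infection classes of the 9.3 list. A harm of higher exposure may well appear as a known reaction in a more severe form, and a test by type alone cannot pick that out.

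**Working it through.** No sample size, power or event count enters this point, so the check is to put the same related serious event through both rules.

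| Related serious event | 9.3 rule (type, protocol list) | 9.1 rule (nature and severity, SmPC) | Agree? |
|---|---|---|---|
| A. In the SmPC, and consistent with it in nature and severity | Expected | Not a SUSAR | Yes |
| B. Type in the SmPC or in a listed class, but more severe than the SmPC describes | Expected | SUSAR | No |
| C. In a listed class, but absent from the SmPC | Expected | SUSAR | No |
| D. In neither the list nor the SmPC | Unexpected by the not-listed wording; arguably expected because the list is open | SUSAR | Indeterminate |

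1. **Row A** shows that the rules meet where the SmPC fully covers the event. Importing the SmPC into the list does no harm there.
2. **Row B** follows because the 9.3 criterion mentions only type. Severity, half of the 9.1 criterion, has no place in it.
3. **Row C** follows because the classes on the list describe complications of the operation and are not drawn from the product's own information.
4. **Row D** follows from the lead-in. The operative test asks whether the type is listed, while the lead-in says that the list is not exhaustive.

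**What happens next in rows B and C.** Under the 9.3 rule for serious adverse events, no individual report goes to the REC or sponsor. Under the SUSAR route, the sponsor hears within one working day, the REC within 15 days, and the MHRA on an expedited basis. The outcome depends on which definition the person classifying the event uses. In every row the event still enters the combined report to the data monitoring committee.

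**Exposure, as context for row B.** Appendix 1 gives a maximum total of 9688 mg over 6 hours, which reproduces from the stated maxima: 2332 + 6 × 1226 = 9688. The largest entries in Table 7 give 1851 + 6 × 855 = 6981 mg. Appendix 1 sets the maximum against 6000 mg in an 8-hour period for the meningitis schedule. Both totals exceed that figure. No view on dose is taken here; the figures show only why severity relative to the SmPC is a relevant criterion.

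**The case against.** The strongest reply is that the SUSAR route stands on its own. SUSAR is defined once, in 9.1, and nothing in 9.3 says that the rule for serious adverse events overrides it. Read together, events in rows B and C are SUSARs and are reported, whatever the list says. They are missed only if staff carry the list across to the SUSAR decision.

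This stands, and it limits the consequence. A reader might infer that 9.3 lets related serious events go unreported, or that they never reach the REC or sponsor. The documents do not support that. Besides the SUSAR duty, the data monitoring committee sees all events in aggregate, 9.3 has a trigger for higher-than-expected rates, and 9.4 provides for the Chief Investigator to review specific serious events and for periodic unblinded safety review.

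The reply does not remove the contradiction. The list sits directly above the SUSAR paragraph, and 9.4 sends the Principal Investigator to 9.3. For each SUSAR, 9.3 also asks whether the event was expected or unexpected, although a SUSAR is unexpected by definition. The aggregate safeguards are thin: section 9 gives no meeting schedule and no expected rates for the trigger, and section 12 does not anticipate that the pilot will be monitored. The sponsor has a say on causality under 9.1, but the 9.3 rule does not send it individually the events that the Chief Investigator has screened out.

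Three further objections have weight.

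- A reader might infer that, with an open list, no event can ever be shown to be unlisted. That goes too far: on a plain reading, an event in neither the list nor the SmPC is not listed. Indeterminate is the right word.
- The SmPC is not among the documents, so no named event, haemorrhage for example, can be shown to be classified differently. The divergence is shown for kinds of event only.
- The protocol considers dose-related events unlikely, and the comparator's 4-hourly schedule also differs from the 8-hourly licensed dosing in 8.2. Departure from the licensed schedule therefore does not by itself single out the infusion arm.

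The study is not a CTIMP (section 2.1), but the protocol adopts the SUSAR definition and expedited reporting, so its own rules should agree.

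**Conclusion.** The point holds as an internal contradiction in safety reporting. Sections 9.1 and 9.3 give opposite answers for two kinds of related serious event (rows B and C) and an unclear answer for a third (row D). Section 9.4 adds a reference that section 9 does not identify.

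The supportable consequence is conditional. If staff apply the 9.3 list, such events can escape individual, expedited reporting to the REC, sponsor and MHRA. If they apply the 9.1 definition, the events are reported individually. Either way, they reach the data monitoring committee in aggregate.

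The number of events affected cannot be derived, because the documents give neither the SmPC text nor expected event rates. The conclusion rests only on the wording of 9.1, 9.3 and 9.4 and needs no assumption about what the SmPC lists. It does not touch the trial's estimates or analyses. It is more than a missing detail, because two stated rules classify the same event differently.

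**What to change.** Reconcile 9.1, 9.3 and 9.4 with two changes to 9.3.

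1. State that, for any serious event judged related to study drug, expectedness is decided only by the 9.1 test: nature and severity against the SmPC, named as the Reference Safety Information to which 9.4 refers. State that the list of post-operative complications does not make such an event expected.
2. Close the list by deleting the phrase in its lead-in that leaves it open.

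Merely confining the list to unrelated events would do little, since 9.3 does not require unrelated events to be reported individually anyway. Section 8.3 already says that an SmPC will be used, so no new document is needed.

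The cost is about two sentences and a few more individual reports in a 90-patient trial. No dose, endpoint or analysis changes.

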## 9.4 Responsibilities

### Principal Investigator (PI):

Checking for AEs and ARs when participants attend for treatment / follow-up.

1. Using medical judgement in assigning seriousness, causality and expectedness using the Reference Safety Information approved for the trial.
2. Ensuring that all planned recording and reporting procedures for SAEs AND SUSARs as detailed in section 9.3 are adhered to. Ensuring that SUSARs are chased with Sponsor if a record of receipt is not received within 2 working days of initial reporting.

### Chief Investigator (CI) / delegate or independent clinical reviewer:

1. Clinical oversight of the safety of patients participating in the trial, including an ongoing review of the risk / benefit.
2. Using medical judgement in assigning seriousness, causality and expectedness of SAEs where it has not been possible to obtain local medical assessment.
3. Using medical judgement in assigning expectedness.
4. Immediate review of all SUSARs.
5. Review of specific SAEs and SARs in accordance with the trial risk assessment and protocol as detailed in the Trial Monitoring Plan.

### Trial Steering Committee (TSC):

In accordance with the Trial Terms of Reference for the TSC, periodically reviewing safety data and liaising with the DMC regarding safety issues.

Data Monitoring Committee (DMC):

In accordance with the Trial Terms of Reference for the DMC, periodically reviewing unblinded overall safety data to determine patterns and trends of events, or to identify safety issues, which would not be apparent on an individual case basis.

## 9.6 Pregnancy reporting

Pregnancy will not be reported in this trial

## 9.7 Overdose

Overdose will be reported by the anaesthetist as this person is the only person to be administering drug. The anaesthetist will be provided contact details for the PI to be notified. Any overdosed patients will be withdrawn from the trial

## 9.8 Reporting urgent safety measures

If any urgent safety measures are taken the CI/Sponsor shall immediately and in any event no later than 3 working days from the date the measures are taken, inform the relevant REC of the measures taken and the circumstances giving rise to those measures.

## 9.9 The type and duration of the follow-up of subjects after adverse events.

Follow-up care for subjects following an adverse drug reaction will be one week.

Adverse events will be identified by review of patient's medical notes.

# 10 STATISTICS AND DATA ANALYSIS

## 10.1 Sample size calculation

This study is a pilot study intending to recruit 90 patients. We require 60 patients with blood samples collected for pharmacokinetic analysis. In approximately 30% of patients it is not possible to obtain blood samples for intra-operative technical reasons.

The full study sample size will be based on the following data:

- Alternative hypothesis: Pharmacodynamic target (4xMIC90 free serum concentrations) based continuous antibiotic dosing of antibiotic prophylaxis reduces the rate of surgical site infection after colorectal surgery by 50% when compared against standard antibiotic prophylaxis dosing regimes.

Justification: Ceftriaxone reduces surgical site infection in colorectal surgery by 39% compared to other cephalosporin regimes (odds ratio 0.61). It is believed this benefit is achieved by obtaining optimal PD targets. The PD target approach to antibiotic prophylaxis investigated in this study is attempting to obtain an equivalent benefit seen from ceftriaxone, without using ceftriaxone. We expect this 39% benefit to be restricted to patients who have operations over 2 hours. As 73% of patients have operations over 2 hours we expect the reduction in SSIs to be 53% (39/73).

Treatment Effect or Alternative Hypothesis: is this the smallest size of effect that would be of clinical interest- how is this justified in the form of appropriate references, pilot data or clinical arguments.

- Null Hypothesis: Pharmacodynamic target (4xMIC90 free serum concentrations) based continuous antibiotic dosing of antibiotic prophylaxis does not reduce the rate of surgical site infection after colorectal surgery when compared against standard antibiotic prophylaxis dosing regimes i.e. there is an absolute difference in response rates between arms of zero.
- Significance level: 0.05.
- Power: 90%
- Adjustments to sample size based on interim analysis(es)
- SSI rate in standard treatment group (operations > 2 hours)
  - 16.5% (estimated from elective patients only)
- SSI rate in investigation group: 50% of standard group=8.25%

## 10.2 Planned recruitment rate

This pilot study plans to recruit 1 patient per week.

## 10.3 Statistical analysis plan

### 10.3.1 Summary of baseline data and flow of patients

- Variables to be used to assess baseline comparability of the randomised groups
  - Age
  - Sex
  - Smoker
  - BMI
  - Charlson Comorbidity Index
  - Respiratory tract disease
  - Urinary tract disease
  - Diabetes
  - Most recent colorectal surgery
  - Previous hospital stay
  - Indication for surgery
  - Haemoglobin
  - eGFR
  - Albumin
  - MRSA status
  - ASA score
  - NNIS score

[figure not shown]
A consort flow diagram (<http://www.consort-statement.org/>) will be produced, as per the figure below.

**CONSORT**  
TRANSPARENT REPORTING of TRIALS

**CONSORT 2010 Flow Diagram**

### 10.3.2 Primary outcome analysis

Statistical analyses of the primary outcome:

- Surgical site infection within 30 days of colorectal surgery will be analysed by comparing proportions.

### 10.3.3 Secondary outcome analysis

Secondary outcomes will be analysed by comparing proportions.

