
Secondary
	
To reduce the rate of all infections after colorectal surgery.
 
To reduce antimicrobial consumption after colorectal surgery
 
To reduce length of hospital stay after colorectal surgery
 
To reduce mortality after colorectal surgery
 
To reduce anastomotic leakage after colorectal surgery
 
To improve quality of life after colorectal surgery
 
To reduce the cost of healthcare treatment associated with colorectal surgery
 
To investigate if pre-operative antibiotic resistance, as determined by antibiotic susceptibility testing of rectally colonising Enterobacteriaceae, is predictive of a patients risk of a post-operative surgical site infection.
 
To investigate the exposure-response relationship for antibiotic prophylaxis in the prevention of surgical site infection prevention after colorectal surgery.
	
All infections within 30 days of operation.
 
Antimicrobial consumption within 30 days of operation.
 
Length of hospital stay after operation
 
Mortality after operation at one year.
 
Radiological or clinically diagnosed anastomotic leakage
 
Quality of life scores pre-operatively and post operatively at 30 days.
 
Cost of healthcare treatments after operation at 30 days.
 
See Table 5
 
See Table 5

Medicinal Product	Cefuroxime 1.5g powder for solution for injection or infusion
Formulation, Dose, Route of Administration	
Formulation
 
Cefuroxime: Each vial contains, as the active ingredient, cefuroxime sodium for injection 1578mg equivalent to 1500mg of cefuroxime respectively
 
Dose
 
Standard treatment
 
 
• 1.5 grams 4 hourly.
 
 
Intervention treatment:
 
 
• A maximum loading dose of cefuroxime 2332 mg
 
• A maximum hourly dose on continuous infusion of 1226 mg/hour. These doses will be administered for a maximum of 6 hours.
 
 
Route of administration
 
Intravenous

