### 3.2 Secondary objectives

To determine if pharmacodynamic target (4xMIC90 free serum concentrations) based continuous antibiotic dosing of antibiotic prophylaxis reduces the rate of all in-patient infections after colorectal surgery when compared against standard antibiotic prophylaxis dosing regimens.

To determine if pharmacodynamic target (4xMIC90 free serum concentrations) based continuous antibiotic dosing of antibiotic prophylaxis reduces the in-patient consumption of antibiotics after colorectal surgery when compared against standard antibiotic prophylaxis dosing regimens.

To determine if pharmacodynamic target (4xMIC90 free serum concentrations) based continuous antibiotic dosing of antibiotic prophylaxis reduces the length of hospital stay after colorectal surgery when compared against standard antibiotic prophylaxis dosing regimens.

To determine if pharmacodynamic target (4xMIC90 free serum concentrations) based continuous antibiotic dosing of antibiotic prophylaxis reduces mortality after colorectal surgery when compared against standard antibiotic prophylaxis dosing regimens.)

To determine if pharmacodynamic target (4xMIC90 free serum concentrations) based continuous antibiotic dosing of antibiotic prophylaxis reduces anastomotic leak after colorectal surgery when compared against standard antibiotic prophylaxis dosing regimens.

To determine if pharmacodynamic target (4xMIC90 free serum concentrations) based continuous antibiotic dosing of antibiotic prophylaxis improves quality of life after colorectal surgery when compared against standard antibiotic prophylaxis dosing regimens.

To determine if pharmacodynamic target (4xMIC90 free serum concentrations) based continuous antibiotic dosing of antibiotic prophylaxis reduces the cost of healthcare treatment after colorectal surgery when compared against standard antibiotic prophylaxis dosing regimens.

To determine if pre-operative antibiotic resistance, as determined by antibiotic susceptibility testing of rectally colonising Enterobacteriaceae, is predictive of a patients risk of a post-operative surgical site infection.

To determine the exposure-response relationship for antibiotic prophylaxis in the prevention of surgical site infection prevention after colorectal surgery.

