#### 3.5 Secondary endpoints/outcomes

- All in-patient infections within 30 days of operation
- All in-patient antimicrobial consumption within 30 days of operation.
- Length of hospital stay after operation
- Mortality after operation at one year.
- Anastomotic leak within 30 days of operation
- Quality of life scores pre-operatively and at 30 days.
- Cost of healthcare treatments after operation at 30 days.

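### Section 10.3.3 compares all secondary outcomes as proportions, but four of the seven are quantities with no cut-point or other method given

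*Combined protocol and SAP*

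**What the plan says.** The whole of section 10.3.3 is one sentence: "Secondary outcomes will be analysed by comparing proportions".

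Among the seven secondary endpoints in section 3.5 are these four:

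- "All in-patient antimicrobial consumption within 30 days of operation"
- "Length of hospital stay after operation"
- "Quality of life scores pre-operatively and at 30 days"
- "Cost of healthcare treatments after operation at 30 days"

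Section 3.2 states the matching objectives as comparisons between regimens. For example, it asks whether the intervention "reduces the length of hospital stay after colorectal surgery" and whether it "improves quality of life after colorectal surgery". The Trial Summary words the cost objective as "To reduce the cost of healthcare treatment associated with colorectal surgery".

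**The concern.** A rule for comparing proportions can be applied to days, scores or pounds only after each patient has been classed as above or below some value. If the plan gives no such value, someone has to choose it later, or the analyst has to depart from the plan. Either way the analysis of these endpoints is not pre-specified.

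The target also changes. A difference in the proportion staying longer than some number of days is not a reduction in length of stay, and it depends on the number chosen. The same holds for consumption, cost and quality of life. Quality of life raises a further question, because the score is collected before and after surgery and the plan does not say how the first measurement is used. A 90-patient pilot also has little information to give away.

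**Working it through.** **Step 1. Classify the endpoints in section 3.5.**

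| Endpoint | Type | Does the 10.3.3 rule fit? |
|---|---|---|
| In-patient infections | Binary if counted as patients with at least one (unit not stated) | Yes, on that reading |
| Antimicrobial consumption | Amount | No |
| Length of stay | Duration | No |
| One-year mortality | Binary | Yes |
| Anastomotic leak | Binary | Yes |
| Quality of life | Score at two times | No |
| Cost | Money | No |

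The rule does not fit 4 of 7.

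**Step 2. Look for a cut-point or method elsewhere.**

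- Section 3.4 calls for aggregation by percent, but only for the primary endpoint.
- Section 10.5 (adjusted analysis) is marked not applicable. Sections 10.9 (other considerations) and 10.11 (economic evaluation) each say none.
- Section 11.1 names EQ-5D, antibiotic consumption and length of stay as data to collect. It gives no threshold for any of them, and no unit or setting for consumption.
- The documents' only unit cost is about £5000 per surgical site infection (sections 1 and 2).

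Nothing in sections 3, 7, 10 or 11 fills the gap.

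**Step 3. Information lost by splitting.** For a normal outcome with a shift between arms, a cut at percentile p keeps the fraction φ(z_p)² / [p(1 − p)]. At the median, φ(0) = 0.3989, so the fraction is 0.1592 / 0.25 = 0.637, or about 64%. A quartile cut gives 0.539.

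In terms of power, take 45 per arm (90 split equally), two-sided 0.05 and a standardised difference of 0.5. Section 10.1 lists 0.05 for the full study, so using it for the pilot is an assumption.

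- Comparing means: the expected test statistic is 0.5 × √(45/2) = 2.37, which gives power of about 66%.
- Median split: the proportions are Φ(0.25) = 0.599 and 0.401, which gives power of about 46%.

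**Step 4. Check what should replace the rule for length of stay.** Not every analysis in days improves on a split. The assumed shape is lognormal stay with median 7 days and log-SD 0.6, rounded to whole days, 45 v 45, with stay 30% shorter in one arm. Simulated results were:

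| Method | Difference detected | Wrongly detected when there is none |
|---|---|---|
| Bootstrap CI, difference in medians | 35% | 1% |
| Chi-square on a median split | 57% | – |
| Bootstrap CI, difference in means | 76% | 7% |
| Mann-Whitney | 78% | – |

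The weak result for medians is not surprising. For a normal shift the sample median has efficiency 2/π = 64%, the same as a median split, and whole-day values can make it worse. The shape is assumed, so the ordering matters more than the exact percentages.

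**The case against.** The best defence is that this is a pilot. Its 90 patients are set by the need for 60 with blood samples, and the full-study inputs listed in section 10.1 use none of these four endpoints. The sentence in 10.3.3 closely follows the one for the primary outcome in 10.3.2, so careless drafting is plausible. Simple descriptive summaries would be enough, and baseline adjustment of EQ-5D is good practice rather than the only cure.

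Much of this stands, and it limits how serious the point is. It does not remove the mismatch. Section 3.2 sets comparative objectives, 10.3.3 prescribes a comparison, and the plan does not say that these outcomes will only be described.

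Two stronger readings are tempting, and the documents support neither.

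- A reader might infer that cut-points will be picked to favour one arm, and that false positives will follow. The plan describes no such practice. Section 7.4 delays final unblinding until the analysis data set is locked, and a cut-point fixed without knowledge of arm would not bias the test. The plan does not require cut-points to be fixed in that way, and section 7.3.1 puts the randomisation record in a database open to researchers. That leaves a gap in protection; it is not evidence of selection.
- A reader might infer that section 10.11 cancels the cost endpoint. It may exclude only a formal economic evaluation. What can be said is that cost is an endpoint with no method and no source of unit costs.

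**Conclusion.** The point holds and should be fixed. One rule is applied without exception to seven endpoints, and for four of them it is the wrong kind of analysis for the stated objective. This rests on the text alone and needs no assumption about the data.

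The loss of information does depend on shape. The 64% kept by a median split, and the fall in power from 66% to 46%, apply to a normal outcome with a shift; other shapes can lose more or less. The primary comparison of surgical site infection is not touched, so the trial's main result is not in question.

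**What to change.** Limit the comparison of proportions in 10.3.3 to in-patient infection (patients with at least one), anastomotic leak and one-year mortality. Analyse the other four on their own scale with 95% confidence intervals:

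- **Length of stay:** Mann-Whitney with a Hodges-Lehmann difference in days, or a mean difference. Show medians and interquartile ranges, and report in-hospital deaths by arm. Do not use a bootstrap interval for the difference in medians (step 4 of the working).
- **Consumption:** mean difference in antibiotic-days. Check that the case report form records antibiotic dates and setting. Section 3.5 restricts this endpoint to in-patient use and the Trial Summary does not, so the two should be aligned.
- **EQ-5D:** compare the day-30 score (visit 5) between arms, adjusting for the pre-operative score already collected. Amend 10.5 to allow this one adjustment. Report deaths and missing scores by arm, since 10.8 plans no handling of missing data.
- **Cost:** either a mean difference with a stated unit-cost source and 10.11 clarified, or remove cost from the Trial Summary, 3.2 and 3.5.

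Other suitable summaries on the original scale would also cure the defect. The change costs a few sentences and a little more analysis, with no new visits. Its limits are that the EQ-5D comparison covers only patients with a follow-up score, and that cost, if kept, will be partial and should be labelled so.
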